	Further secondary outcomes – as nutritional and morbidity indicators - will be analysed using logistic and linear regression as appropriate. To compare individual's changes in nutrition/morbidity categories as an effect from treatment McNemar's test will be applied. The analysis after 6 and 12 month of follow-up will be complemented by generalized estimating equation (GEE) models with independent correlation structure and empirical estimators to account for missing data.				
	Nonlinear mixed-effects modeling will be used to determine pharmacokinetic parameters.				

GCP statement	This study will be conducted in compliance with the protocol, the current version of the Declaration of Helsinki, ICH-GCP E6 (R2) as well as all national legal and regulatory requirements.
Key explanation for the inclusion of children	This study will involve school-aged children, since an infection with T . trichiura occurs most often in children and they are further the main target group of deworming campaigns.
Recruitment procedure	The parallel group trial will be conducted as a multi-country study with two settings in Africa and one in Asia recruiting each 600 community members:
	West African setting: Côte d'Ivoire
	• East African setting: Pemba (Zanzibar, Tanzania)
	Asian setting: Lao PDR
	The DF study will be embedded in the trial and implies the recruitment of an additional 160 school-aged children (6-12 years) to be able to include 40 children per arm in Côte d'Ivoire.
	The studies will be conducted in areas with moderate to high T. trichiura endemicity (communities with a prevalence $\geq 25\%$) identified from earlier studies and/or based of experience of the local collaborating teams. They will be implemented as community-based studies in order to recruit participants from a broad age range (6-60 years). Ideally, entire communities with a population size of < 1000 inhabitants will be included in the study for prescreening and identification of T. trichiura cases to avoid potential selection bias of households. To identify all potentially eligible households of the respective communities and its composition in terms of age groups a preceding population census will be conducted.
Coverage of damages	Winterthur Police Nr. 4746321, BERACA Côte d'Ivoire, No: to be issued

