All trial participants will further be asked about existing clinical symptoms before drug administration. Additionally, they will be asked to provide subjective short-term (*e.g.* convenience of treatment) and long-term (*e.g.* effectiveness in reducing symptoms) treatment satisfaction embedded in the re-assessment questionnaires. As a measure of patient-rated physical functioning and wellbeing all children (6-16 years) will be administered a questionnaire before, 6 and 12 months after treatment, based and adapted from tools already validated in schoolaged children from rural settings in Côte d'Ivoire [25] and pre-tested in a comparable school-aged population not otherwise involved in this trial. To adjust for known influencing factors with regard to reinfection and morbidity [26, 27] in the subsequent analysis and to identify risk factors for residual infections [28] a household-based questionnaire will be administered to one adult member of each participating household, assessing information on socioeconomic characteristics, access to sanitation and water facilities as well as hygiene behavior.

DF study with school-aged children

Embedded in the parallel group trial a randomized-controlled DF study assessing ascending doses of ivermectin co-administered with a single dose of albendazole will be implemented. The study is designed as a four-armed trial including ascending doses of ivermectin co-administered with the standard dose of albendazole (arm 1–3) and one placebo arm serving as a comparator (arm 4) (Figure). 160 school-aged children infected with *T*. *trichiura* will be randomly assigned to arm 1–4. Baseline and screening procedures are identical to the parallel group study. Children in arm 1-3 will be micro sampled on different time points between treatment day 0 and day 2 (at 0, 1, 2, 3, 4, 5, 6, 7, 9, 24, 48 hours post-dosing) in order to obtain pharmacokinetic data while children in arm 4 will provide finger-prick blood samples at day 0 only for RDT assessments.

Figure 3. Efficacy, safety and pharmacokinetics of ivermectin-albendazole co-administration: dose-finding study flow.

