4.4 Measure to minimize bias

For each study (*i.e.* parallel group trial and DF study) independently study participants eligible for treatment will be randomly assigned to one of the treatment arms using a computer-generated stratified block randomization code. The random allocation sequence with varying random blocks of four or eight and stratified by 2 levels of baseline infection intensity (light: <1000 EPG, and moderate plus heavy: ≥ 1000 EPG *T. trichiura* infections) will be provided by a statistician. The treatment arms will have an equal number of participants with light infection intensity, although the number of light versus moderate/heavy infections are not expected to be equal in each arm, depending on the distribution of infection intensity in the recruited cohort. The parallel group trial will be double blinded (*i.e.* study participants and the trial team/researchers conducting the treatment and assessing the outcomes will be blinded) using repacked tablets including appearance-matched placebos while the DF study will be single blinded (*i.e.* all outcome assessors except the investigators who provide the treatment and the study

Page 28 of 176

participants who get either active or placebo tablets matching in appearance will be blinded) due to the nature of this study (*i.e.* including ascending doses).

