5.1 Recruitment

The study will be carried out in community members aged 6–60 years in areas with moderate to high *T. trichiura* endemicity (communities with a prevalence $\geq 25\%$) identified from earlier studies and/or based on experience of the local collaborating teams. The trial will be implemented as community-based study in order to recruit participants from a broad age range (6–60 years). Ideally, entire communities with a population size of < 1000 inhabitants will be included in the study for pre-screening and identification of *T. trichiura* cases to avoid potential selection bias of households. To identify all potentially eligible households of the respective communities and its composition in terms of age groups a preceding population census will be conducted.

All adult community members, including parents/caregivers of minor participants, will be invited to participate in an information meeting to explain the purpose and procedures of the study, including potential benefits and risks. Parents/caregivers/potential participants will be encouraged to ask questions in an open discussion forum. During this session, they will be informed of preventive actions they can take to help protect their children from acquiring *T. trichiura* and other STH infections in the future (*e.g.* adequate food, preparation and defecation behavior).

Those parents/caregivers and their children who are interested in the study will be invited to complete the process of informed consent. See section 9.3 for details on obtaining informed consent. Only those participants who have written informed consent will be assessed for study eligibility criteria during screening procedures.

Page **31** of **176**

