Questionnaires on physical functioning and treatment satisfaction will be evaluated by creating summary scores by summing up and transforming the single question scores according to the following formula: [(actual raw score-lowest possible raw score)/(possible raw score range)]*100 [25].

Nutritional and morbidity indicators will be analysed using logistic and linear regression as appropriate. To compare individual's changes in nutrition/morbidity categories as an effect from treatment McNemar's test will be applied. The analysis after 6 and 12 month of follow-up will be complemented by generalized estimating equation (GEE) models with independent correlation structure and empirical estimators to account for missing data.

AEs will be evaluated descriptively as the difference of proportion reporting AEs before and after treatment.

On the basis of the LC-MS/MS measurements, the following PK parameters for plasma will be calculated:

C_{max} maximal plasma concentration

 t_{max} time to reach C_{max}

Page 38 of 176

AUC area under the curve, from 0 to 24h and 0 to infinity

T_{1/2} elimination half-life

T and AUC above minimal inhibitory concentration (MIC)

 C_{max} and T_{max} will be observed values derived from the plasma concentration time profile. AUC and $T_{1/2}$ will calculated with the software WinNonlin (Version 5.2, Pharsight Corporation, USA) using compartmental analysis. The elimination half-life will be estimated by the equation: $T_{1/2} = \ln 2/\lambda$, where λ will be determined by performing a regression of the natural logarithm of the concentration values during the elimination period.

Further PK analysis will be undertaken fitting a structural compartmental PK model with the software NONMEM 7 [39] via nonlinear mixed effects modeling (allowing for both between patient variation and random effects). This model will describe the plasma drug levels in time, allowing one to investigate variation between patients in drug levels. In addition, PK/PD analysis will be undertaken via NONMEM to investigate the drivers of cure and/or burden reduction and potentially any covariates with drug levels.

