7.4 Description of data management and data quality control

The investigators are responsible for an adequate data quality. Prior to the initiation of the study, a short investigator's meeting will be held with the investigators and their study coordinators and a member from Swiss TPH. This meeting will include a detailed discussion of the protocol, performance of study procedures (standard operating procedures (SOPs) from previous studies available on site), CRF completion, and specimen collection and diagnostic methods.

The data produced from this research project will fall into the following categories:

- Eggs counts of *T. trichiura*, *A. lumbricoides* and hookworm and infection status with *S. stercoralis* based on participants' stool samples analyzed using the Kato-Katz and Baermann technique, respectively, before (baseline) and at 3 time points after treatment (follow-ups after 3 weeks, 6 and 12 months). Presence of fecal occult blood and elevated calprotectin levels will be evaluated and recorded applying RDTs on the same stool samples and assessment time points.
- 2. Personal information such as name, age, gender and household composition of trial participants.
- 3. Anthropometric and clinical characteristics of the trial participants collected using the study's CRF such as weight, height, skinfold thickness, blood pressure, temperature, hemoglobin level, infection status with *Plasmodium spp.* and filariasis, any abnormal medical condition or chronic disease as well as pregnancy in female participants 10 years and above.
- 4. Number and type of AEs registered in the CRF actively probed for 3 and 24 hours after treatment. The same data will be collected during the collection of the first sample at the 3-week follow-up.
- 5. Scales for participant-rated treatment satisfaction and self-rated physical functioning in school-aged children captured on different time points (i.e. 3 weeks and 6 months and baseline, 6 and 12 months after treatment, respectively) and recorded on the CRF.
- 6. Concentration levels of blood and biochemical parameters together with indicators for micronutrient status before (baseline) and at 3 time points after treatment (follow-ups after 3 weeks, 6 and 12 months).
- 7. Household-level data on socioeconomic characteristics, presence and use of water and sanitation as well as hygiene-related attitudes and practices.

Page 39 of 176

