	Geometric and arithmetic mean egg counts will be calculated for the different treatment arms before and after treatment to assess the corresponding ERRs. Bootstrap resampling method with 5,000 replicates will be used to calculate 95% confidence intervals (CIs) for ERRs. Morbidity indicators (continuous measurements) will be compared in a first step within and between groups using independent and paired t-test statistics while chi-square testing will be performed for binary/categorical outcomes (e.g. anemia, blood in stool). To compare individual's changes in morbidity categories as an effect from treatment McNemar's test will be applied. In a second step, adjusted repeated measures linear and logistic regressions using generalized estimating equation (GEE) models will be performed to assess development of morbidity indicators within each individual and related factors be investigated.
GCP statement	This study will be conducted in compliance with the protocol, the current version of the Declaration of Helsinki, ICH-GCP E6 (R2) as well as all national legal and regulatory requirements.

Key explanation for the inclusion of children	This study will involve school-aged children, since an infection with T. trichiura occurs most often in children and they are further the main target group of deworming campaigns.			
Recruitment procedure	 The longitudinal trial will be conducted as a multi-country study with two settings in Africa and one in Asia recruiting each 600 community members: West African setting: Côte d'Ivoire East African setting: Pemba (Zanzibar, Tanzania) Asian setting: Lao PDR 			
	The studies will be conducted in areas with moderate to high T. trichiura infection intensities (communities with a prevalence $\geq 25\%$) identified from earlier studies and/or based of experience of the local collaborating teams. They will be implemented as community-based studies in order to recruit participants from a broad age range (6-60 years). Ideally, entire communities with a population size of < 1000 inhabitants will be included in the study for pre-screening and identification of T. trichiura cases to avoid potential selection bias of households.			
Coverage of damages	Winterthur Police Nr. 4746321, National Insurance Corporation of Tanzania (to be issued)			

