5.1 Recruitment

The study will be carried out in community members aged 6–60 years in areas with moderate to high *T. trichiura* infection intensities (communities with a prevalence $\geq 25\%$) identified from earlier studies and/or based of experience of the local collaborating teams. The trial will be implemented as community-based study in order to recruit participants from a broad age range (6–60 years). Ideally, entire communities with a population size of < 1000 inhabitants will be included in the study for pre-screening and identification of *T. trichiura* cases to avoid potential selection bias of households. Another option might be to run the trial at schools and invite school-aged children and one adult for each child of the same household.

All adult community members, including parents/caregivers of minor participants, will be invited to participate in an information meeting to explain the purpose and procedures of the study, including potential benefits and risks. Parents/caregivers/potential participants will be encouraged to ask questions in an open discussion forum. During this session, they will be informed of preventive actions they can take to help protect their children from

acquiring *T. trichiura* and other STH infections in the future (e.g., adequate food preparation and defecation behavior).

Those parents/caregivers and their children who are interested in the study will be invited to complete the process of informed consent. See section 9.3 for details on obtaining informed consent. Only those participants who have written informed consent will be assessed for study eligibility criteria during screening procedures.

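### Household-questionnaire variables are shared by all enrolled household members, but no planned analysis accounts for household clustering, so intervals for these factors come out too narrow if the named methods are applied as they stand

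*Combined protocol and SAP*

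**What the plan says.** Section 4.3.1 of the Swiss-approved protocol, with near-identical text in the three country protocols, gives the household questionnaire two uses. One is to adjust for known influences on reinfection and morbidity. The other is stated as "to identify risk factors for residual infections [28] a household-based questionnaire will be administered to one adult member of each participating household". Section 7.4 of the Swiss, Côte d'Ivoire and Laos protocols classes the answers as "Household-level data on socioeconomic characteristics, presence and use of water and sanitation as well as hygiene-related attitudes and practices".

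Several enrolled members per household are to be expected. Section 5.1 says that, ideally, "entire communities with a population size of < 1000 inhabitants will be included in the study". Section 5.1 of the Pemba protocol adds a school-based option, to "invite school-aged children and one adult for each child of the same household". Allocation is by individual: "study participants eligible for treatment will be randomly assigned to one of the treatment arms" (section 4.4).

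The analysis methods named are:

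- **Cure rates** (7.3 and the SAP efficacy analysis): logistic regression, with age, sex and weight in the adjusted protocol model. Pemba adds community and height.
- **Nutrition and morbidity** (7.3, Swiss, Côte d'Ivoire, Laos): logistic and linear regression, complemented at 6 and 12 months by "generalized estimating equation (GEE) models with independent correlation structure and empirical estimators to account for missing data".
- **Morbidity, Pemba** (synopsis, Statistical Analyses): repeated-measures GEE regressions that "will be performed to assess development of morbidity indicators within each individual and related factors be investigated".

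None of these passages mentions a household random effect, a household cluster or household-robust standard errors. No model is written for the residual-infection risk factors. The SAP covers the three-week data, which include day-21 infection status, but describes no risk-factor analysis.

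**The concern.** A variable measured once per household is constant across its members. If infection or morbidity is also correlated within households, because members share soil, latrine, water and behaviour, then each further member adds less than one person's worth of information about that variable. Ordinary regression counts every member in full. So does a GEE whose empirical variance is clustered on the person: it allows for repeated visits by the same person but not for relatives living together. Standard errors for latrine, water source or wealth effects are then too small, and such factors are declared associated with residual infection, or with morbidity in Pemba, more often than the nominal 5%. What is at stake is the credibility of the reported risk factors, not the drug comparison.

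**Working it through.** **The plan's own figures.** Section 7.2 sizes only the treatment comparison: 30% versus 50%, 90% power, two-sided 5%. With the unpooled formula, (1.960 + 1.282)² × (0.30×0.70 + 0.50×0.50) / 0.20² = 10.507 × 0.46 / 0.04 = 120.8, so 121 per arm; 121 / 0.85 = 142.4, so 143.

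For 12 months, with 10% reinfection per half-year and re-treatment of positives at the same cure rate:

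- Albendazole: (0.27 + 0.73×0.30) × 0.90 = 0.4401.
- Combination: (0.45 + 0.55×0.50) × 0.90 = 0.6525.
- The same sample-size formula gives 110.2, so 111 per arm.

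All three figures reproduce. The documents state no power, precision or design effect for household-level factors.

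**Inputs for the check.** From the documents: the exposure is constant within household, allocation is individual, there are 600 participants per country, and loss to day 21 is 15%, leaving 600 × 0.85 = 510. Assumed, because the documents give neither: m enrolled members per household and the ICC of the outcome within household.

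**Formulas**, for a covariate constant within equal-sized households:

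- Design effect: DE = 1 + (m − 1) × ICC
- Naive interval width as a share of the correct width: 1/√DE
- True type I error at nominal 5%: 2 × [1 − Φ(1.96/√DE)]
- Effective sample size: 510/DE

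| m | ICC | DE | Naive / correct width | Too narrow by | Type I error | Effective n of 510 |
|---|---|---|---|---|---|---|
| 1 | any | 1.00 | 1.000 | nil | 5.0% | 510 |
| 2 | 0.05 | 1.05 | 0.976 | 2% | 5.6% | 486 |
| 2 | 0.10 | 1.10 | 0.953 | 5% | 6.2% | 464 |
| 3 | 0.10 | 1.20 | 0.913 | 9% | 7.4% | 425 |
| 3 | 0.20 | 1.40 | 0.845 | 15% | 9.8% | 364 |
| 5 | 0.20 | 1.80 | 0.745 | 25% | 14.4% | 283 |
| 5 | 0.30 | 2.20 | 0.674 | 33% | 18.6% | 232 |

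DE depends on m and ICC, not on the total, so recruiting 600 per country does not remove the problem.

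**Simulation check** (1000 runs per row, about 510 people, 60% residual infection, each household exposed with probability one half, no true effect; the GEE columns use two visits per person):

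| m | ICC | Ordinary logistic | GEE, empirical variance by person | GEE, empirical variance by household |
|---|---|---|---|---|
| 2 | 0.10 | 6.0% | 5.8% | 4.5% |
| 3 | 0.10 | 7.5% | 7.7% | 5.2% |
| 3 | 0.20 | 10.6% | 10.2% | 5.7% |
| 5 | 0.20 | 14.5% | 17.3% | 5.1% |

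The last two columns use the same working-independence model; only the cluster for the variance changes. For the individually randomised treatment in the same runs, ordinary logistic regression and the person-clustered GEE gave 4.4% to 5.6%.

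**The case against.** The strongest reply is that the plan contains no faulty model to correct. The written logistic models compare cure rates between arms, and none of their covariates comes from the household questionnaire. A reader might infer that the plan specifies a risk-factor model that treats household members as independent. The documents do not support that: for residual infection no model is written at all, so the gap there is one of specification. This part of the reply stands, and it makes the narrowness of the intervals conditional on the named methods being used as they are.

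A reader might also infer that working independence in the GEE is itself the error. It is not: with empirical variance clustered on the household it is valid. The Swiss, Côte d'Ivoire and Laos protocols leave the cluster unit open. The individual is suggested only by the Pemba synopsis, whose wording describes what is assessed and does not mention empirical variance.

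Nor do all the protocols search for risk factors of morbidity. Section 4.3.1 uses the questionnaire to adjust for influences on reinfection and morbidity, and where a variable is only an adjuster its own interval is not the target. The wider reading rests on Pemba alone, where factors related to morbidity are to be investigated.

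The size may also be small. Only people aged 6 to 60 with at least two of four slides positive and at least 100 EPG are enrolled, and community prevalence need only reach 25%, so enrolled members will be fewer than household members. Five per household would require large households or high prevalence. This also stands, and it is why the table starts at nil.

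What the reply does not remove is that the exposure is shared, several members per household are expected, and none of the named methods uses the household as the cluster.

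**Conclusion.** The point holds as a conditional one. If the named methods are applied as they stand, intervals for household-questionnaire variables are too narrow wherever more than one member is enrolled and outcomes correlate within households. Under the assumed ranges the shortfall runs from nil (m = 1), through 2% (m = 2, ICC 0.05), 9% (m = 3, ICC 0.10) and 15% (m = 3, ICC 0.20), to 33% (m = 5, ICC 0.30), with type I error between 5.0% and 18.6%. These figures assume equal household sizes and a covariate constant within household. The documents do not show which row applies.

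A reader might infer that the primary result or the sample size is compromised. Neither is: treatment is allocated by individual, and the simulated error for treatment stayed near nominal. Household risk factors are not among the listed objectives or endpoints, so this is a cheap improvement to an exploratory analysis.

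**What to change.** In section 7.3 of each protocol, state that any model reporting effects of household-questionnaire variables uses the household as the cluster for the empirical (sandwich) variance, with all enrolled members and all their visits nested in it. This covers residual infection at day 21 and the related factors in the Pemba morbidity GEE. Working independence can stay. The residual-infection model has to be written down in any case, and this sentence belongs with it. Pemba's community covariate does not do this job, because it leaves correlation between members of the same household unaddressed.

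The cost is somewhat wider intervals for household factors. The Pemba questionnaire form (Appendix 13.1) already has a household ID field, and household composition is among the data listed in section 7.4 of the other protocols.
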